5.1. Inclusion Criteria

Each participant must meet **all** of the following study criteria to be enrolled in this study:

1. Capable of giving signed informed consent as described in Appendix 1 which includes compliance with the requirements and restrictions listed in the informed consent form (ICF) and in this protocol. Informed consent will be obtained prior to any Screening procedures and in accordance with national, local, institutional guidelines.
2. Hospitalized within the last 36 hours.
3. Receiving any form of supplementary oxygen therapy at baseline.
4. Confirmed COVID-19 viral infection by RTPCR at screening.
5. Age:
 - a. 18-65 years old, OR
 - b. >65 year-olds can be included after DMC approval (see section 10.1.5)
6. Contraception:

Male participants:

A male participant must agree to use contraception as detailed in **Appendix 2** of this protocol during their participation in this study and for a period of 90 days after the last dose; and also refrain from donating sperm during this period.

Female participants:

A female participant is eligible to participate if she is not pregnant, and at least one of the following conditions applies:

- a. Not a woman of child-bearing potential (WOCBP) as defined in **Appendix 2**.

OR

- b. A WOCBP who agrees to follow the contraceptive guidance in **Appendix 2** during their participation in this study for at least 1 complete menstrual cycle (≥ 30 days) after last dose.

5.2. Exclusion Criteria

Participants meeting **any** of the following criteria will be excluded from the study:

1. Contraindications/hypersensitivity to *P histicola* or any of the capsule excipients
2. Patients with chronic hypoxia or underlying significant chronic respiratory disease (such as COPD, Pulmonary Fibrosis, or Bronchiectasis).
3. Admission to ICU at time of screening.
4. Mechanically ventilated, on CPAP, or on non-invasive ventilation at the time of screening.
5. Patient is taking a systemic immunosuppressive agent such as, but not limited to, oral steroids, methotrexate, azathioprine, ciclosporin, or tacrolimus, unless these are given as part of COVID standard of care treatment.
6. Patient has a diagnosed primary immunodeficiency.
7. Patient has a diagnosis of HIV/AIDS
8. Patient has pre-existing known chronic kidney disease stage 4 or 5 or requiring renal replacement therapy (i.e. estimated glomerular filtration rate (eGFR) <30ml/min/1.73m²); [Laboratory results within the last 48 hours may be used].
9. Patient has pre-existing known significant liver disease with Alanine aminotransferase (ALT) or aspartate aminotransferase (AST) $\geq 5.0 \times$ upper limit of normal (ULN); [Laboratory results within the last 48 hours may be used].
10. Patient has pre-existing known significant gastrointestinal tract disease expected to affect absorption within the small intestine (e.g. short bowel syndrome, inflammatory bowel disease affecting the small intestine, gastroparesis); or prior malabsorptive bariatric surgery that could interfere with GI delivery and transit time.
11. GI signs or symptoms equivalent to CTCAE v5.0, gastrointestinal disorders, grade 3 or 4 event.
12. Patient has pre-existing known substantially impaired cardiac function or pre-existing clinically significant cardiac diseases, including unstable angina or acute myocardial infarction ≤ 6 weeks prior to Screening.
13. Currently participating in an interventional clinical trial (observational studies allowed).
14. Moribund at time of screening
15. Female participant who is currently pregnant at time of screening
16. Female participant who is unwilling to stop breastfeeding during treatment period
17. Any medical history or clinically relevant abnormality that is deemed by the principal investigator and/or medical monitor to make the patient ineligible for inclusion because of a safety concern.
18. Unwilling to comply with study procedures, including follow-up, as specified by this protocol; or unwillingness to cooperate fully with the investigator.

5.3. Lifestyle Restrictions

Participants must refrain from consuming acidic drinks for 1 hour either side of dosing and from eating 2 hours before dosing and 1 hour after dosing.

5.4. Screen Failures

Screen failures are defined as participants who consent to participate in the clinical study but are not subsequently randomly assigned to study intervention/entered in the study. A minimal set of screen failure information is required to ensure transparent reporting of screen failure participants to meet the Consolidated Standards of Reporting Trials (CONSORT) publishing requirements and to respond to queries from regulatory authorities. Minimal information includes demography, screen failure details, eligibility criteria, and any SAEs.

If subjects fail the screening procedures then they will not be allowed to be re-screened.

6. Study Interventions

Study intervention is defined as any investigational intervention(s), marketed product(s), placebo, or medical device(s) intended to be administered to a study participant according to the study protocol.

6.1. Study Interventions Administered

All study interventions in this study will be administered orally. EDP1815 will be supplied as capsules that are enteric coated to release the contents in the duodenum and jejunum. The drug product is manufactured by [REDACTED].

The EDP1815 drug product is available as enteric coated hydroxylpropyl methylcellulose (HPMC) hard capsules in white to off-white color. The formulation of EDP1815 consist of freeze-dried powder of *P. histicola* and excipients. The excipients include mannitol, magnesium stearate and colloidal silicon dioxide. Each EDP1815 PIC contains 8.0×10^{10} cells of *P. histicola*.

The matching placebo are identical in appearance but do not contain *P. histicola* or any other bacteria. Matching placebo is supplied by [REDACTED]. The placebo excipients include microcrystalline cellulose and magnesium stearate.

Treatment with EDP1815 or placebo will be twice daily for 6 doses and then once daily for 11 doses (14-day total course). There should be a minimum of two hours between the twice daily doses. For subjects who are discharged within the 14-day period, medication will be dispensed to take at home.

Table 3: Treatment Arms

Arm	Dosage
EDP1815	1.6 x 10^{11} cells as 2 capsules twice daily for 6 doses, then once daily to 14 days
Placebo	2 capsules twice daily for 6 doses, then once daily to 14 days

Participants must refrain from consuming acidic drinks 1 hour either side of dosing and from eating 2 hours before dosing and 1 hour after dosing. Refer to the Pharmacy Manual for further details.

6.2. Preparation/Handling/Storage/Accountability

All capsules will be supplied in blister packs and must be kept in controlled conditions of 2-8°C while at the study site.

1. The investigator or designee must confirm appropriate temperature conditions have been maintained during storage and transit for all study interventions received and any excursions are reported and resolved before use of the study intervention.
2. Only participants enrolled in the study may receive the study intervention and only authorised site staff may supply the study intervention. While at the study site, all study intervention must be stored in a secure, environmentally controlled, and monitored area

(manual or automated with the ability to show minimum and maximum temperatures daily), in accordance with the labelled storage conditions with access limited to the investigator and authorised site staff.

3. If the study intervention is given to participants to take at home, the participants should be instructed to take it straight home from the hospital, and then to store it at home in the refrigerator and out of reach of children.
4. The investigator is responsible for study intervention accountability, reconciliation, and record maintenance (i.e. receipt, reconciliation, and final disposition records).
5. Further guidance and information for the final disposition of unused study interventions are provided in the Pharmacy Manual.

6.3. Measures to Minimize Bias: Randomization and Blinding

This is a randomized controlled study and therefore, the treatment allocation is random. Randomized treatment ensures minimisation of selection bias, so that the individuals in the two treatment groups are not systematically different, other than the treatment that they receive. A paper randomisation will be used to assign participants to study interventions.

Blind Break (Scratch-off code breaks)	A scratch-off code break that contains the study intervention assignment for each participant will be provided to each site investigator. The scratch-off code breaks will be retained by the investigator (or representative) in a secured area. In case of an emergency, the investigator has the sole responsibility for determining if unblinding of a participant's treatment assignment is warranted. Participant safety must always be the first consideration in making such a determination. If a participant's treatment assignment is unblinded, the Sponsor must be notified within 24 hours after breaking the blind. Once the study is complete, all scratch-off code breaks (revealed and non-revealed) must be inventoried and returned to the Sponsor.
--	---

The investigational drug blind shall not be broken by the investigator unless information concerning the study intervention is necessary for the medical treatment of the participant.

For unblinding a participant, the investigational drug blind can be obtained by scratching off the blinded area to reveal the treatment information.

The Sponsor must be notified immediately (within 24 hours) if the investigational drug blind is broken. The date, time, and reason the blind was broken must be recorded on the appropriate Case Report Form (CRF).

6.4. Study Intervention Compliance

Drug supplies will be counted and reconciled at the study site before being returned.

The investigator must maintain 100% accountability for all study intervention received and dispensed during the entire duration of the study. Proper drug accountability includes, but is not limited to:

- Continuously monitoring expiration dates if expiry date or retest date is provided to the investigator.
- Frequently verifying that actual inventory matches documented inventory.
- Verifying that the log is completed for the drug lot used to prepare each dose.
- Verifying that all containers and/or packs used are documented accurately on the log.
- Verifying that required fields are completed accurately and legibly.

If any dispensing errors or discrepancies are discovered, the Sponsor must be notified immediately.

The investigator must maintain a current inventory (Drug Accountability Log) of all study intervention delivered to the site, inventory at the site, dispensing log, and participants' use records. This log must accurately reflect the drug accountability of the study intervention at all times. The following information will be recorded at a minimum: protocol number and title, name of investigator, site identifier and number, description of study intervention, kit numbers, expiry or retest date (if applicable) and amount dispensed, and the date and amount returned to the site by the participant, including the initials of the person dispensing and receiving the study intervention. The log should include all required information as a separate entry for each participant to whom study intervention is dispensed.

Prior to site closure or at appropriate intervals, a representative from the Sponsor or its designee will perform clinical study material accountability and reconciliation before clinical study materials are returned to the Sponsor or its designee for destruction. The investigator will retain the original documentation regarding clinical study material accountability, return, and/or destruction, and copies will be sent to the Sponsor.

The investigator will be notified of any change in expiry date or retest date of clinical study material during the study conduct. On expiry date notification from the Sponsor or designee, the site must complete all instructions outlined in the notification, including segregation of expired clinical study material for return to the Sponsor or its designee for destruction. In the event of expiry date extension of supplies already at the study site, supplies may be relabeled with the new expiry date at that site. In such cases, the Sponsor or its designee will prepare additional labels, certificates of analyses, and all necessary documentation for completion of the procedure at the sites.

6.5. Concomitant Therapy

All standard of care therapy is permitted for use any time during the study.

There are no contraindications to treatment. There are no prohibited concomitant medications and no anticipated drug-drug interactions. Of note, no significant inhibition or induction of any of the CYP450 enzymes were observed *in vitro* after EDP1815 treatment.

Any medication or vaccine (including OTC or prescription medicines, probiotics, and/or herbal supplements) that the participant is receiving at the time of enrolment or receives during the study must be recorded along with:

- Reason for use
- Dates of administration including start and end dates
- Dosage information including dose and frequency

Any diagnostic, therapeutic, or surgical procedure performed during the study period should be recorded, including the dates, description of the procedure(s), and any clinical findings, if applicable. The Medical Monitor should be contacted if there are any questions regarding concomitant or prior therapy.

6.6. Study stopping criteria

6.6.1. Safety

Safety data will be evaluated on an ongoing basis by a Data Monitoring Committee (DMC) which will consist of at least; a chairperson, 2 physicians independent of the study team, and an unblinded statistician. The DMC support staff for the blinded sessions will include the Principal Investigator, the Evelo medical monitor, a blinded statistician, and an Evelo clinical operations representative. The DMC will review the data in a blinded manner but can request unblinded data if required. Any unblinded data will be reviewed only by the chairperson, 2 independent clinicians, and the unblinded statistician. The DMC can halt the study at any point for safety concerns. Further details can be found in the DMC charter.

The study should be terminated if either of the following conditions are met:

1. One (or more) subjects on treatment with EDP1815 has symptoms of a clinically significant bacteremia and has a positive blood culture for the EDP1815 strain of *P. histicola*. (Note: the study will be paused and dosing held in all participants while identifying the specific strain of *P. histicola*).
2. The DMC believe that EDP1815 is potentially detrimental to patient outcomes.

6.7. Intervention after the End of the Study

No specific interventions are planned after the end of the study, which is the visit 28 days after the last dose of the study drug (Day 42).

7. Discontinuation of Study Intervention and Participant Discontinuation/Withdrawal

7.1 Discontinuation from Study Treatment and/or Withdrawal from the Study

Participants may discontinue from study treatment or withdraw from the study at any time and for any reason without prejudice to their future medical care by the investigator or at the study site. Every effort should be made to keep participants in the study. The reasons for participants discontinuing treatment and/or withdrawing from the study will be recorded in the CRF. A participant may discontinue from the study drug or withdraw for the following reasons:

1. The participant does not meet the protocol inclusion or exclusion criteria.
2. The participant is non-compliant with the protocol.
3. The participant is admitted to ICU. At this point, dosing for this individual subject will be stopped, but they will remain in the study until Day 42 for data collection where practical. However, if the subject is eligible for another interventional trial, they may be enrolled into this trial after discussion with the chief investigators. The participant is deemed to have completed this study at the point of signing the informed consent of this other study.
4. The participant has a serious or intolerable AE that in the investigator's opinion requires discontinuation from study treatment or withdrawal from the study (see section 7.2).
5. The participant has laboratory safety results that reveal clinically significant changes from the baseline values that are not, in the opinion of the investigator, explained by COVID-19 infection or CRCs.
6. The participant is lost to follow-up.
7. Other reasons (e.g. pregnancy).
8. The participant withdraws consent, or the investigator or sponsor decides to discontinue the participant's participation in the study.

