
To identify clinical or biochemical predictors of response to EDP1815, and to confirm lack of systemic absorption.	
Statistical significance of each potential predictor-treatment interaction in exploratory models based on the final selected model for the primary efficacy analysis.To identify the presence of EDP1815 in stool and/or blood using PCR primers

Overall Design:

This is a randomized, placebo-controlled clinical study to assess the safety and efficacy of EDP1815 in patients hospitalized with COVID-19 infection. The study is designed to evaluate the efficacy of EDP1815 at reducing time to resolution of symptoms, preventing progression of COVID-19 symptoms and preventing COVID-Related Complications (CRC). The study will be fully blinded to the participants, investigator, and sponsor. This is a pilot study with a primary objective of investigating the potential of EDP1815 in the prevention of COVID-19 disease progression. The secondary objective is to evaluate multiple endpoints for clinical relevance and sensitivity, while informing the sample size for future studies. Where possible, data will be taken from assessments performed as part of the participant's routine clinical care in this pragmatic study.

Participants who are hospitalized with confirmed COVID-19 disease and are confirmed to be eligible for the study will be randomized to either the active (EDP1815) or placebo group (1:1 randomization), in addition to standard of care. Dosing will be initiated on a twice daily regime for the first 3 days (6 doses) and then once daily for the remaining 11 days (14 days total treatment course). The trial hypothesis is that treatment with EDP1815 in hospitalized patients reduces oxygen requirements by normalizing the exaggerated host immune response to COVID-19. This will be measured by assessing the ratio of the Oxygen Saturation (SpO₂) / Fraction of Inspired Oxygen (FiO₂), which is a validated measure of severity of ARDS.

Dosing will be stopped if participants are admitted to ICU, efficacy and safety data will continue to be collected according to the schedule of activities, where practical. However, if the participant is eligible for another interventional trial at this point, they may be enrolled into it, and withdrawn

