4.4. End of Study Definition

A participant is considered to have completed the study if he/she has completed the treatment period and completed their final safety follow-up visit 28 days after their last dose. A participant is also considered to have completed the study if they are withdrawn from the study. If a participant is admitted to ICU and is enrolled in a subsequent study then they are deemed to have completed this study at the point of signing the informed consent.

The end of the study is defined as the date of the last visit of the last participant in the study or last scheduled procedure shown in the Schedule of Activities (SoA).

5. Study Population

This protocol contains participants with a confirmed diagnosis of COVID-19 viral infection.

Potential participants will be identified by reviewing hospital admissions, as well as reviewing the positive results from COVID-19 testing. Potential participants will be referred to the research team if they are interested in participating in this clinical trial. Once contact has been made with the patient, the research team will outline and explain the aims of the trial. An electronic or paper copy of the Patient Information Sheet (PIS) will then be given to the patient who will have the opportunity to consider the information and discuss the trial with the trial staff, and raise any queries before consenting to participate in the trial.

Prospective approval of protocol deviations, also known as protocol waivers or exemptions, is not permitted.

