5.3.3.5 Overall Survival and Intubation and Mechanical Ventilation Free Survival

Overall survival (OS) is defined as the time in days from randomization until death by any cause.

Intubation and mechanical ventilation free survival (IMVFS) is defined as the time in days from randomization until the earliest event of death by any cause or requirement for intubation and/or mechanical ventilation as indicated by the first occurrence of a WHO OSCI score of 6 or above.

Participants who complete the 42-day study period or prematurely withdraw from the study without experiencing the relevant event will be censored on the date of study completion/withdrawal.

Participants who prematurely withdraw from treatment but remain in the study will not be censored and will continue to be followed up until the first occurrence of the relevant event, study completion or withdrawal from the study.

Time to the relevant event will be calculated as:

$$\text{Time to event (days)} = \text{Date of event/censoring} - \text{date of randomization} + 1$$

5.3.3.6 Time to Discharge, Time to SpO2 ≥94% on Room Air and Time to Recovery

Time to discharge is defined as the time in days from randomization until the date of discharge.

Time to SpO2 ≥94% on room air is defined as the time in days from randomization to the first day at which an SpO2 measurement ≥94% on room air is reported after which there were no further requirements for oxygen therapy during the study.

Time to recovery is defined as the time in days from the date of symptom onset until the first day on which a WHO OSCI score of 0 is reported with no further increase above 0 during the study.

Participants who die during the study before the relevant event occurring will be given a status of 'death' which will be considered as a competing risk rather than an event or a censored observation in the analysis.

Participants who are still alive at the end of the 42-day study period or who withdraw prematurely from the study for reasons other than death without experiencing the relevant event will be censored on the date of study completion/withdrawal.

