7.3 Missing Data

7.3.1 General

Participants who discontinue treatment before the end of the scheduled 14 days treatment period will remain in the study and complete assessments as scheduled unless they die, start an alternate experimental treatment, or withdraw consent. Data collected at scheduled visits following discontinuation of study treatment will be included in all analyses.

Participants who are discharged from hospital before the end of the 42-day study period will be asked to complete a participant diary everyday with details of their symptoms, any AEs experienced and any changes to their concomitant medications.

Imputation rules for individual variables with missing data have been provided in [Section 5.3](#).

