9.2 Primary Efficacy Analysis

9.2.1 Primary Efficacy Estimand

The primary estimand will be the effect of EDP1815 compared to placebo on the change from baseline to trough S/F ratio in Days 1-14.

The population summary measure of interest will be the difference in mean change from baseline in trough S/F between EDP1815 and placebo.

Intercurrent events will be accounted for in the following manner:

Table 9 Intercurrent Event Strategies for the Primary Estimand

Intercurrent event	Strategy to account for intercurrent event
Treatment discontinuation before the end of the 14-day treatment period	Treatment policy Trough S/F ratio will be taken as the lowest recorded value on or off treatment
Death prior to day 14	Composite Trough S/F ratio will be imputed as 0
Discharge prior to day 14	While-on-treatment Trough S/F ratio prior to discharge will be used. Participants will be assumed to remain above trough value after discharge.
Withdrawal from the study prior to day 14.	While-on-treatment Trough S/F ratio prior to starting study withdrawal will be used

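### ICU patients who join another trial leave follow-up, and survival, ventilation, OSCI and recovery endpoints then treat that exit as unrelated to prognosis

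*Protocol*

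**What the plan says.** **Default after ICU admission.** Under Protocol 7.1, dosing stops, but "they will remain in the study until Day 42 for data collection where practical".

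**Exit.** The same item allows an eligible ICU patient to enter another interventional trial after discussion with the chief investigators. It then closes this study for them: "The participant is deemed to have completed this study at the point of signing the informed consent of this other study". Protocol 4.4 agrees: "If a participant is admitted to ICU and is enrolled in a subsequent study then they are deemed to have completed this study". The Synopsis labels the event differently: "if the participant is eligible for another interventional trial at this point, they may be enrolled into it, and withdrawn". Protocol 4.1 also calls it withdrawal. SAP 7.3.1 says that participants who stop treatment stay in the study "unless they die, start an alternate experimental treatment, or withdraw consent", without limiting that exit to ICU patients.

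**Handling after exit.**
- Overall and ventilation-free survival (SAP 5.3.3.5): those who "prematurely withdraw from the study without experiencing the relevant event will be censored on the date of study completion/withdrawal". Protocol 9.4.1.2 and SAP Table 12 agree.
- Times to discharge, SpO2 of at least 94% and recovery (SAP 5.3.3.6, Table 13): censored at withdrawal.
- OSCI (SAP Table 11): excluded from the study day onward.
- S/F ratio at Days 4, 7, 10 and 14 (SAP Table 10): excluded.
- Primary trough (SAP Table 9): "Trough S/F ratio prior to starting study withdrawal will be used". For a death before Day 14, by contrast, "Trough S/F ratio will be imputed as 0".

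**The concern.** The Protocol opens this exit only after clinical failure. Those who take it are therefore at higher risk of death or ventilation than those who remain under observation. Kaplan-Meier, Cox and Fine-Gray estimates are unbiased only if censoring carries no information about the outcome, given the model covariates. Those covariates are all baseline factors, so they cannot capture ICU admission. Mortality and ventilation rates would read too low, and the cumulative incidence of discharge and recovery too high.

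SAP 9.3.1.2 says of the S/F data that values missing because another experimental treatment was started cannot be taken as missing at random. It does not carry that through to the time-to-event or OSCI endpoints.

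The results are meant to inform later studies. Efficacy data also go to the DMC when it considers adding 40 participants (SAP 7.4.3). Outcomes that were never collected cannot be recovered later by analysis.

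**Working it through.** **1. Is there a planned safeguard?** The primary sensitivity analyses (SAP 9.2.3) address the zero for death and new standard of care. The only analysis triggered by withdrawal is an MMRM for S/F ratio, run if at least 10% withdraw before Day 14 (SAP 9.3.1.2). The same section calls that model type inappropriate for these data. Oxygen days and pyrexia days have worst-case variables for withdrawal (SAP 5.3.3.7, 5.3.3.8). Nothing comparable exists for survival, ventilation-free survival, OSCI, discharge, SpO2 or recovery.

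**2. Mortality level.** The documents give no rates, so these are assumptions: ICU share p = 15-25%, mortality after ICU m = 30-50%, share of ICU patients leaving u = 25-50%, exit about one day after ICU admission, and all deaths following ICU.

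True Day 42 mortality = p × m. If exits precede deaths, Kaplan-Meier mortality ≈ p(1−u)m / (1−pu). Example: 0.25 × 0.50 × 0.50 / (1 − 0.125) = 0.0625 / 0.875 = 7.1%. Results from 1,500 simulated trials of 60 for each row:

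| p | u | m | Formula: true → KM | Simulated: true → KM | Simulated fall (points) |
|---|---|---|---|---|---|
| 15% | 25% | 30% | 4.5 → 3.5 | 4.5 → 3.5 | 1.0 |
| 15% | 25% | 50% | 7.5 → 5.8 | 7.7 → 6.0 | 1.7 |
| 15% | 50% | 30% | 4.5 → 2.4 | 4.5 → 2.4 | 2.1 |
| 15% | 50% | 50% | 7.5 → 4.1 | 7.4 → 3.9 | 3.5 |
| 25% | 25% | 30% | 7.5 → 6.0 | 7.4 → 5.9 | 1.5 |
| 25% | 25% | 50% | 12.5 → 10.0 | 12.5 → 10.0 | 2.5 |
| 25% | 50% | 30% | 7.5 → 4.3 | 7.5 → 4.3 | 3.2 |
| 25% | 50% | 50% | 12.5 → 7.1 | 12.4 → 7.1 | 5.3 |

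The share of all participants leaving by this route is pu, from 0.15 × 0.25 = 3.75% to 0.25 × 0.50 = 12.5%. The route alone may therefore not reach the 10% trigger.

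**3. Treatment contrast.** Same formula with m = 50%; a simulation of 200,000 per arm agrees to within about 0.2 points.
- *Same ICU rate and same exit in both arms:* the level falls, but no difference is created.
- *ICU 30% placebo, 15% active (true difference 15.0 − 7.5 = 7.5 points):* at u = 25%, 12.2 − 5.8 = 6.3 from unrounded values (simulated 6.2). At u = 50%, 8.8 − 4.1 = 4.8 (simulated 4.8). At u = 75%, 4.8 − 2.1 = 2.7 (simulated 2.6).
- *No treatment effect, ICU 20% in both arms, exit 25% versus 75%:* 7.9% versus 2.9% (simulated 7.8% versus 3.0%), against a true 10% in each arm.

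**4. Primary endpoint.** The plan's own half-width reproduces: t(0.975, 58) × 100 × √(4/60) = 2.002 × 25.82 = 51.7. A death by Day 14 that is missed after exit is scored at the pre-exit trough instead of 0. That raises a 30-patient arm mean by trough/30: 90/30 = 3.0, 150/30 = 5.0. With a pre-exit trough of 100, the simulated between-arm shift was at most about 2 units.

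**The case against.** **Stopping at another experimental treatment is a stated choice.** Protocol Tables 6 and 7 specify while-on-treatment for it, because later outcomes would mix in the other trial's drug. This stands for the S/F endpoints, where moving to treatment policy is a debatable trade. It does not justify ceasing to collect vital status.

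**Withdrawn participants may still be followed.** Protocol 7.3 asks them to complete the follow-up visit assessments, and the follow-up calls include the ordinal scale. But 4.4 and 7.1 call these patients completers, so it is unclear that 7.3 applies. The survival and time-to-event analyses censor at completion or withdrawal in any case.

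**The primary endpoint is partly covered.** SAP 9.2.3 plans an analysis that uses the lowest reading before death instead of 0, which removes the contrast between an observed and a missed death. This stands, although it does not recover lower S/F values after exit.

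**This is an unpowered, descriptive pilot.** At 7.4% mortality, the 95% half-width for a difference between arms of 30 is 1.96 × √(2 × 0.074 × 0.926 / 30) ≈ 13 points, wider than the bias shown. That is fair on precision, but a known and avoidable bias should not be carried into planning figures.

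**Conclusion.** The concern holds for overall survival, ventilation-free survival in patients not yet at OSCI 6, OSCI, and the discharge, SpO2 and recovery times. Under the assumed ranges, Kaplan-Meier Day 42 mortality is understated by about 1 to 5 points. The upper end needs the highest assumed uptake and ICU mortality; at 25% uptake the fall is 1.0 to 2.5 points. The treatment contrast is biased if ICU admission or exit differs by arm. The effect on the Fine-Gray endpoints was not quantified.

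Three stronger readings are tempting, and the documents do not support them:
- *Every ICU patient is censored at transfer.* The default is follow-up to Day 42 where practical. Exit is optional and needs eligibility, discussion and consent elsewhere.
- *The primary result is compromised.* The shift is 3 to 5 units on an arm mean per missed early death, against a half-width of 51.7 at SD 100.
- *Unequal access to other trials across sites biases the arms.* Sites receive complete randomization blocks and the study is double-blind (SAP 5.2), so site differences alone fall on both arms.

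This is a cheap improvement, not a flaw that undermines the trial.

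**What to change.** Leave the option to join another trial unchanged.

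1. **Follow-up.** In Protocol 1.1, 4.1, 4.4 and 7.1 and SAP 7.3.1, use one label for this exit. Continue record extraction of vital status, OSCI, oxygen and discharge status to Day 42 unless consent to data collection is withdrawn. The Schedule of Activities already marks these items as taken from the patient record where available. State that passive follow-up after study dosing has stopped is not concurrent interventional participation, which 1.1 and 4.1 prohibit.
2. **Survival endpoints.** Analyse overall and ventilation-free survival on all collected follow-up, with censoring at exit as a sensitivity analysis.
3. **OSCI, discharge, SpO2 and recovery.** Keep the stated strategy if preferred, but add a sensitivity analysis that uses the post-exit data or treats exit after ICU admission as unfavourable.
4. **Primary endpoint.** Add a sensitivity analysis that scores a known death by Day 14 as 0 whether or not another trial was joined.
5. **Consistency.** Align Protocol Tables 6-7 and 9.4.1.2 with SAP 5.3.3.5, 5.3.3.6 and Tables 9-13.

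The cost is a protocol clarification, a consent sentence and SAP wording, with no added visits or procedures. The downside is that outcomes after exit may reflect the other trial's treatment, which the censor-at-exit analysis helps a reader judge.
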